Where and when will this procedure take place?

Participants will be recruited from the pool of people who have signed up for the mentoring group through WCNC. WCNC will advertise the mentoring group through their website and marketing materials as they do for other education classes they offer. Fathers who sign up for or express interest in the group program will be provided information about the associated research study by information posted on the WCNC website or by WCNC staff through verbal interaction, emails and/or flyers handed out at the clinic. Social media (e.g., Instagram/Facebook) postings made by department and clinic accounts will also be used to promote the study. Participation in the study is not required for those attending the mentoring group. Fathers attending the mentoring groups will be provided with links to listen to podcast episodes. Podcast listeners who have consented to participate in the study will be invited through the podcast website to complete brief satisfaction surveys about each podcast episode using their study ID.

Who will conduct this procedure?

Personnel

[name]

External User

Personnel
[name]

External User

Personnel
[name]

External User

Indicate the frequency and duration of visits/sessions as well as the subject's total time commitment for the study.

Describe how the data will be collected (i.e. in person or online).

Sign-ups for mentoring groups will occur online through the WCNC website.

Will any video, photography, or audio be recorded as part of this procedure?

No

Will data be collected anonymously?

No

Procedure Description
Screening and Consent

This procedure is:

Research Activity Involving Participants, Participants Data, or Biospecimens

This procedure is:

Where and when will this procedure take place?

All those who have decided to take part in the mentoring groups will be assigned an ID by WCNC staff. Potential participants will use this ID to complete an online screener survey. Those who are eligible will then be automatically provided consent information online through Qualtrics. Research staff will notify WCNC staff of the ID numbers of consented participants for management of survey distribution.

Who will conduct this procedure?

Personnel

[name]

Personnel

[name]

External User

Indicate the frequency and duration of visits/sessions as well as the subject's total time commitment for the study.

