Completing the online screening and consent procedure will take 5-15 minutes.

Describe how the data will be collected (i.e. in person or online).

Online

Will any video, photography, or audio be recorded as part of this procedure?

No

Will data be collected anonymously?

No

Procedure Description

Participation in the Mentoring Program

This procedure is:

Research Activity Involving Participants, Participants Data, or Biospecimens

This procedure is:

Where and when will this procedure take place?

Program facilitation will be conducted by trained staff members ([name], [name]) through WCNC – either in-person at clinic facilities or virtually by Zoom depending on health guidelines. Programs will start running in August, 2021, with a new group starting each month.

Who will conduct this procedure?

Personnel

[name]

External User

Personnel

[name]

External User

Indicate the frequency and duration of visits/sessions as well as the subject's total time commitment for the study.

1.5 hours per session, with 8 total sessions. Total time: 12 hours.

Describe how the data will be collected (i.e. in person or online).

Facilitators will be asked to keep attendance data, rate participant engagement, and complete a checklist of program items completed for each week of the intervention. At the end of the mentoring program, facilitators will also be asked to provide their feedback about the supportiveness of the group dynamics.

Will any video, photography, or audio be recorded as part of this procedure?

No

Will data be collected anonymously?

No

Procedure Description

Online Surveys

This procedure is:

Research Activity Involving Participants, Participants Data, or Biospecimens

This procedure is:

Experimental

Where and when will this procedure take place?

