Participants from the mentoring group or who are on a waiting list for the next mentoring group will be invited to complete electronic surveys at four time points over four months, with four weeks between each survey. A WCNC staff member ([name]) will send out a survey link to consented participants at each time point. Surveys will be available through [name]'s CSU Qualtrics account. Participants will enter their unique ID number in each survey so surveys can be linked over time. Surveys will assess demographics and outcomes of interest, including stress, mental health symptoms, parenting knowledge, confidence in parenting, the coparenting relationship, and satisfaction with their social networks. Participants will also be asked about whether or not they listened to podcasts.

Who will conduct this procedure?

Personnel

[name]

Personnel
[name]

External User

Indicate the frequency and duration of visits/sessions as well as the subject's total time commitment for the study.

15-30 minutes for each electronic outcome survey over 4 surveys. Total time: 1-2 hours.

Describe how the data will be collected (i.e. in person or online).

Online through Qualtrics

Will any video, photography, or audio be recorded as part of this procedure?

No

Will data be collected anonymously?

No

Procedure Description
Mentoring Program Satisfaction Surveys

This procedure is:

Research Activity Involving Participants, Participants Data, or Biospecimens

This procedure is:

Experimental

Where and when will this procedure take place?

Participants who have attended the mentoring program will be invited to complete an electronic satisfaction survey through [name]'s CSU Qualtrics account following completion of the group program. Surveys will ask about demographics, what participants liked or didn't like about the program, their perceptions of the group environment, and supportive group dynamics. Participants will also be given a brief (1-2 minute) electronic questionnaire at the beginning of each week of the program assessing their engagement in homework. Survey links will be sent by a member of the WCNC staff ([name]) to maintain separation of participant contact information from data. [name] will manage the data on the research side.

Who will conduct this procedure?

Personnel

[name]

Personnel

[name]

External User

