Identifiable information will only be accessible to WCNC staff. WCNC staff will provide ID numbers to each participant to use for completing their surveys. Research staff will only have access to participant ID numbers paired with survey data, not participant names or contact information. Survey responses will be aggregated for the purposes of reporting to community partners, stakeholders, publications, and grant reports. Given the small sample size, it is possible a person's data could be linked to their demographic information. To mitigate this risk, any data reported by demographic will be withheld if the demographic subgrouping contains a population of 3 or fewer people.

Clinical Trial

Will participants will be prospectively assigned to one or more interventions (including placebo or other control)?

Yes

Will the study evaluate the effects of the intervention on health-related outcomes (biomedical or behavioral)?

Yes

Does this study involve an FDA-regulated drug or device?

No

Will the study be conducted as a
Single-Site Clinical Trial

Will this study be posted on ClinicalTrials.gov?

Yes

ClinicalTrials.gov Registration# (or pending)

Pending

Additional information and support available through CSU Quality Assurance:

[contact]

Participant Population

Are you interacting or intervening with participants?

Yes

Provide an estimate of the anticipated participant total.

56

Are you analyzing existing data records or biospecimens?

No

Inclusion and Exclusion Criteria (e.g., Participants must have 20/20 vision, Participants must be 30-45 years of age, etc.) This should match your screening, consent, and recruitment materials.

Please list all inclusion criteria

Participants must be expecting a baby or have a baby less than one year of age and have signed up to participate in the DadSpace mentoring program at WCNC

Please list all exclusion criteria

Less than 18 years of age, non-English-speaking.

What is the rationale for studying the requested group(s) of participants?

These participants comprise the target population of people served by the clinic and the primary focus of the intervention.

Will you use a screening procedure, instruments, tools, questionnaires etc.?

Yes

Describe any planned screening procedures. Attach your screening document(s) (e.g., health history questionnaire), if applicable at the end of the form.

Participants will be screened for inclusion and exclusion criteria as listed above. Screening questions are attached.

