Statistical Design and Power

Study Title: DadSpace: Increasing Community Support Resources for Perinatal Fathers

Study ID: 1754

Date of Plan: 6/14/2021

Statistical Design and Power

We anticipate that by the conclusion of the DadSpace program feasibility trial, 28 fathers will have completed the program as well as pretests and posttests, and 28 fathers will have completed pre- and posttests as wait-list controls. With a moderate effect size of Cohen's $d = .50$, this sample size will provide power = .95 using a 2 (time) by 2 (group) repeated measures ANOVA with stability coefficients of $r = .50$. Power will be lower but still sufficient (.81) to detect a small/moderate effect size of $d = .33$. Given that pilot trials of DadSpace (e.g., *Becoming Fathers*) and focus groups have indicated that DadSpace is likely to be effective, we believe that effect sizes of .40-.50 are likely on each of the primary outcome measures.

In section 4.2, we entered multiple "additional measures," all of which assess program implementation. These measures provide us with feedback as to how the DadSpace program was delivered and received by the participants. Following best practices (e.g., Berkel et al., 2011), this information will serve two purposes: to provide guidance on strengthening the DadSpace program, and to assess how variations in implementation are related to degree of program impact. In order to assess the latter, exploratory correlational analyses will be conducted between implementation variables and gain scores on the pre-/posttest measures of program impact.

<https://doi.org/10.1007/s11121-010-0186-1>

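### The only planned test of program effect is a gain-score comparison; pre-specify a pretest-adjusted model beside it, and let the allocation method decide which is primary

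*SAP*

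**What the plan says.** The SAP (Statistical Design and Power) expects 28 fathers to complete the program with pretests and posttests, and that "28 fathers will have completed pre- and posttests as wait-list controls". Power is computed "using a 2 (time) by 2 (group) repeated measures ANOVA", with stability coefficients of .50, giving .95 at d = .50. No other comparison of program with wait-list appears, and no sensitivity analysis. The remaining analysis is also built on gains: "exploratory correlational analyses will be conducted between implementation variables and gain scores on the pre-/posttest measures of program impact".

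On allocation, the protocol's Clinical Trial section answers Yes to whether participants will be "prospectively assigned to one or more interventions (including placebo or other control"), but gives no method. The Online Surveys procedure describes those surveyed as "Participants from the mentoring group or who are on a waiting list for the next mentoring group". Under Recruitment, "Sign-ups for mentoring groups will occur online through the WCNC website"; under Participation in the Mentoring Program, groups run "with a new group starting each month". Randomization, order of sign-up, group capacity and a father's own choice are not mentioned as the basis for placement.

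Outcome surveys are sent "at four time points over four months, with four weeks between each survey". The SAP's model uses two waves and does not say which survey is the posttest.

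**The concern.** Whether the program improves fathers' short-term outcomes is one of the protocol's primary objectives (Study 1 Objective 2), so the model behind that comparison matters even in a feasibility trial.

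Gain-score and pretest-adjusted analyses of the same data rest on different assumptions about starting differences between arms. Gains assume that any pretest difference would have persisted in full without the program. ANCOVA assumes that it would have shrunk to r times its size. Under random allocation there is no systematic difference, both models are unbiased, and ANCOVA is more precise. Under non-random allocation, each can be wrong where the other is right, and both can be wrong together.

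With one model planned and the allocation method unstated, the assumption goes unchecked. A second model added after results are known would let the choice of analysis follow the answer.

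**Working it through.** **Inputs.** From the SAP: n = 28 per arm, r = .50, d = .50 with power .95. Assumed, because the SAP does not give them: two-sided alpha of .05 and equal SDs (set to 1) at both waves. The pretest gaps below are scenarios; no gap appears in the documents.

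**The SAP's figure.** With f = d/2 = .25, lambda = N × m × f² / (1 - r) = 56 × 2 × .0625 / .5 = 14.0. On 1 and 54 df, power is .957, which matches .95.

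**What that figure means as a difference in change.**
- Var(gain) = 2(1 - r) = 1.00.
- The standard error of the difference in mean gain is sqrt(2/28) = .267.
- A difference in change of Δ has lambda = Δ² × 14, so lambda = 14 corresponds to Δ = 1.0 SD. If d = .50 is instead the difference in change itself, gain-score power is .451.

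**Random allocation.**
- Residual variance given the pretest is 1 - r² = .75, against 1.00 for gains.
- Allowing for the estimated slope with balanced arms, the variance ratio ANCOVA/gain is .75 × (1 + 1/52) = .764, a cut of 23.6%.
- Power below is analytic for gains and simulated for ANCOVA with the slope estimated. Re-runs of the simulation agree within about .01.

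| True difference in change | Gain score | ANCOVA |
|---|---|---|
| .50 SD | .45 | about .555 |
| 1.0 SD (reproduces .95) | .957 | .988 |

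The 95% CI half-width falls from .54 to .47 SD.

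**Non-random allocation, no true effect.** Let the program arm start D higher and let kD remain at posttest without any program effect. Then:
- gain-score bias = kD - D = (k - 1)D;
- ANCOVA bias = kD - rD = (k - r)D;
- ANCOVA minus gain = (1 - r)D, whatever k is. For D = .3 (.5) this is .5 × .3 = .15 (.5 × .5 = .25) SD.

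Rejection rates (nominal 5%) are rounded from simulation. Entries are for D = .3, with D = .5 in brackets.

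| Gap at posttest | Gain bias | Gain rejects | ANCOVA bias | ANCOVA rejects |
|---|---|---|---|---|
| Stable, k = 1 | 0 | 5% | +.15 (+.25) | about 9.5% (17.5%) |
| Shrinks to rD, k = .5 | -.15 (-.25) | 8.5% (15%) | 0 | 5% |
| Gone, k = 0 | -.30 (-.50) | 20% (45%) | -.15 (-.25) | about 10% (17.5%) |

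In the last row both estimates miss in the same direction, so the pair does not bracket the truth.

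**Power is not always higher with ANCOVA.** For a true .50 SD benefit (higher = better), if the program arm starts .3 (.5) SD lower and that gap is stable, ANCOVA has power .31 (.18) against .45 for gains. If the program arm starts .3 SD higher and the gap shrinks to rD, gains have .25 against .55.

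**Chance.** Under random allocation the pretest difference has SD .267. About 26% of trials this size show a pretest difference of .3 SD or more, and in about 26% the two estimates differ by .15 SD or more.

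**The case against.** The strongest reply is that the planned test is not wrong. A gain-score comparison is a recognized choice for a non-randomized wait-list and removes a stable starting difference. On the convention that reproduces the SAP's own .95, ANCOVA adds only about three points of power (.957 to .988). The larger contrast, .45 to about .555, appears only when d is read as the difference in change. The second model cannot show which assumption holds. The allocation method may also be stated in the grant proposal, which the protocol lists as an attachment, or in the section 4.2 to which the SAP refers; neither was supplied.

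Most of this stands. It shows that the gain-score test need not be replaced in every case and that the precision gain may be modest. It does not remove the need to tie the primary model to the allocation method and to fix the companion analysis in advance.

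A reader might go further and infer that, because the clinic staff named as external personnel are barred from survey data, nobody could have assigned fathers on their pretest score. The documents do not support this. The protocol's procedure for concerning survey responses has research staff notify clinic staff about participants with high depression or anxiety scores, and no passage says who assigns.

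**Conclusion.** The point holds as a matter of model choice and pre-specification. If allocation is random, the plan gives up about 24% of estimator variance to a test with no advantage in bias. If it is not, the result rests on one unchecked assumption. A pretest gap of .3 to .5 SD could then move one estimate or the other by .15 to .25 SD, or move gains by .30 to .50 SD and ANCOVA by half that if the gap has gone by posttest. These sizes rest on r = .50, equal SDs, two-sided .05 and the assumed gaps.

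Some stronger readings are not supported:
- A reader might infer that the wait-list is self-selected, or that the gain-score test is invalid. The supplied text does not say how the list is formed, and the test is sound if starting differences are stable.
- A reader might infer that ANCOVA is always safer, or that the two models bracket the truth. The stable and vanishing-gap rows show otherwise.
- A reader might extend the point to the implementation correlations. They are labelled exploratory, and pretest adjustment is not uniformly safer there. For a variable with no true link to impact and assumed correlations of .3 with both pretest and posttest (n = 28), the adjusted analysis rejects 15% of the time against 5% for gains.
- A reader might want expecting or postpartum status added as a covariate. No benefit has been calculated, so it is not part of this point.

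**What to change.** Before outcome data are examined, amend the SAP to:

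1. Name which of the four survey waves is the posttest.
2. State the allocation method, or cite the document that gives it.
3. If allocation is random, make ANCOVA of the posttest on the pretest the primary model. Otherwise keep the gain-score test as primary, or justify ANCOVA instead.
4. In either case, report the other model as a pre-specified sensitivity analysis, with estimates, confidence intervals and pretest means by arm.
5. State that divergence will be read as possible baseline non-equivalence, that a divergence of .15 SD or more arises by chance in about a quarter of randomized trials this size, and that agreement does not prove either assumption.

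The cost is SAP wording and one extra analysis per outcome, since the pretest is already collected. The drawback is that the two answers may differ without showing which assumption is right.

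### The exploratory implementation correlations take no account of mentoring group or pretest; group-recorded measures need group-level handling, and per-father measures need an adjusted analysis alongside gain scores (minor)

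*SAP*

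**What the plan says.** The SAP (Statistical Design and Power) gives the implementation measures two purposes: guidance on strengthening the program, and assessing how variation in implementation relates to impact. Only the second is tied to a statistical method: "exploratory correlational analyses will be conducted between implementation variables and gain scores on the pre-/posttest measures of program impact". No sample size, covariate, group term or error rate is given for it. The sample size has to be inferred from the expectation that "28 fathers will have completed the program as well as pretests and posttests".

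The protocol (Procedures, Participation in the Mentoring Program) shows that the measures sit at two levels. Attendance and engagement ratings belong to a father, as do the weekly homework questionnaire and the satisfaction survey (Mentoring Program Satisfaction Surveys). But facilitators also "complete a checklist of program items completed for each week of the intervention", and at the end "facilitators will also be asked to provide their feedback about the supportiveness of the group dynamics". These two describe the group. Groups start monthly; neither their number nor their size is stated.

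**The concern.** There are two separate gaps.

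First, fathers in one group share the same value, or nearly so, of a group-recorded measure. A correlation across fathers then counts each group value several times. If fathers in a group also gain alike, which is credible after eight discussion sessions together, the p-value and interval are too optimistic.

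Second, a gain score contains the pretest with a negative sign. At a stability of .50 that costs precision compared with adjusting for pretest. It can also produce a correlation with any implementation measure that depends on where fathers started.

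At stake is the reading of which implementation features go with larger program impact. No primary result is affected.

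**Working it through.** **The plan's own figures.** The SAP states none for this analysis. Its power statement concerns the comparison of the program fathers with the wait-list ("28 fathers will have completed pre- and posttests as wait-list controls"): "this sample size will provide power = .95 using a 2 (time) by 2 (group) repeated measures ANOVA", at d = .50. Taking f = d/2 = .25, N = 56, two measurements, r = .50 and two-sided alpha .05 (alpha is assumed), lambda = f² × N × 2/(1 − r) = .0625 × 56 × 2/.50 = 14.0, and the noncentral F with 1 and 54 df gives .957. That agrees with the stated value. The same formula at d = .33 gives lambda 6.10 and power .68, not the stated .81; that is a separate matter. Only r = .50 is carried forward here.

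**Group-recorded measures.** Assumed: 28 fathers in 4 groups of 7 or 7 groups of 4, or 27 fathers in 9 groups of 3; ICC of gains 0 to .20; no true association. Simulated rejection rate when fathers are correlated as separate observations at a nominal 5%:

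| Groups × size | ICC 0 | ICC .05 | ICC .10 | ICC .20 |
|---|---|---|---|---|
| 4 × 7 | .05 | .09 | .13 | .20 |
| 7 × 4 | .05 | .07 | .08 | .13 |
| 9 × 3 | .05 | .06 | .07 | .10 |

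The design effect, 1 + (m − 1) × ICC, shows why. At ICC .20 with groups of 7 it is 1 + 6 × .20 = 2.2, so 28 fathers count as 28/2.2 = 12.7. In the 4 × 7 and 7 × 4 layouts, analysing group means returns the error to .05, but little can be detected. The critical correlation is t/√(G − 2 + t²): with 4 groups, 4.303/√(2 + 18.51) = .95; with 7 groups, 2.571/√(5 + 6.61) = .75.

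**Per-father measures: clustering.** If the measure itself has an ICC of .20, the error with 4 groups of 7 is only .054 to .072 for an ICC of gains of .05 to .20. Group membership matters little here.

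**Per-father measures: precision.** With unit variances, residual variance is 2(1 − r) = 1.00 for gain and 1 − r² = .75 for posttest adjusted for pretest. On gain scores, 28 fathers carry the information of 28 × .75 = 21. For a slope of .4 SD on a measure unrelated to pretest, with residual variance .75 given pretest, simulated power is .51 with gain scores and .61 adjusted.

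**Per-father measures: baseline tracking.** The correlation of pretest with gain is −√((1 − r)/2) = −√.25 = −.50. What follows depends on the model. Simulated type I error with 28 fathers, by the correlation of the measure with pretest:

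| Null model | Method | .2 | .3 | .4 |
|---|---|---|---|---|
| No effect given the observed pretest | Gain score | .08 | .12 | .17 |
| | Pretest-adjusted | .05 | .05 | .05 |
| Measure tracks a stable trait that the pretest records with error | Gain score | .05 | .05 | .05 |
| | Pretest-adjusted | .09 | .15 | .25 |

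Neither method is safe in both rows, and the documents do not say which model applies.

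**The case against.** The strongest reply is that this is a labelled exploratory analysis in a feasibility study, that the choice between change scores and pretest adjustment for a non-randomised predictor is a question of estimand and not an error, and that the cluster figures rest on invented inputs. Most of this stands. The upper figure of 20% needs only 4 groups and an ICC of .20. Monthly starts from August 2021 and an end date of July 30, 2022 could allow about nine or ten groups to finish, so about three fathers per group and an error of 6% to 10%. Group dynamics is also covered in the fathers' own satisfaction survey, so not all information on it is group-level.

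A reader might infer three stronger points that the documents do not support:

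- That the SAP decides to treat fathers as independent. It is silent; a literal reading leads there, but cluster handling is not excluded. The figure of 28 is likewise inferred, since wait-list fathers who attend later could add data.
- That gain scores are the wrong method and must be replaced. The second table shows that replacement could raise false positives; the obvious example, more stressed fathers attending more, could fit either model.
- That these correlations will steer revision of the program. The SAP ties them only to relating implementation to impact; guidance on strengthening is the other stated purpose of the implementation information.

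What survives is that the sentence does not separate measures that need different analyses.

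**Conclusion.** The point holds and is minor. For the checklist and the facilitator feedback, a father-level correlation overstates the evidence whenever gains cluster by group: about 6% to 20% error for a nominal 5%, under assumed layouts of 4 to 9 groups and an ICC of .05 to .20, and none at ICC 0. For attendance, engagement, homework and satisfaction, relying on gain scores alone gives up a quarter of the information at the SAP's own r = .50. Whether it also biases the result, or whether adjustment would, cannot be settled from the documents. That argues for showing both analyses, not for exchanging one for the other.

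**What to change.** Amend the SAP sentence as follows, keeping the exploratory label:

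- List which implementation measures are recorded per group and which per father.
- Relate per-group measures to group mean gains, or only describe them if there are few groups.
- For each per-father measure, report the gain-score correlation and a regression of posttest on the measure with pretest as covariate, both with 95% confidence intervals. State in advance that results differing between the two will be treated as inconclusive.

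The cost is a few lines of text, no new data, one further analysis (and one degree of freedom) per per-father measure, and wide intervals for the group-recorded measures.
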